## 4.5.2. Exclusion Criteria

Subjects meeting one or more of the following criteria cannot be enrolled in this clinical study:

1. Known hypersensitivity to IMP ingredients or history of a significant allergic reaction to any drug as determined by the investigator, such as anaphylaxis requiring hospitalization.
2. Breastfeeding female or subject intending to become pregnant or breastfeed.
3. History of or a current immunosuppressive condition (e.g. human immunodeficiency virus [HIV] infection, congenital, acquired).
4. Criterion modified per amendment.
  - 4.1. Positive blood testing for hepatitis B surface antigen or hepatitis C virus (antibody, confirmed by hepatitis C virus RNA positivity). Note: Subjects with a resolved hepatitis A at least 3 months prior to screening can be screened.
5. Criterion modified per amendment.
  - 5.1. History of malignancy within the past 5 years (except for carcinoma in situ of the uterine cervix, basal cell carcinoma of the skin that has been treated with no evidence of recurrence, prostate cancer medically managed through active surveillance or watchful waiting, and squamous cell carcinoma of the skin if fully resected and ductal carcinoma in situ).
6. Criterion modified per amendment.
  - 6.1. Clinically significant abnormalities, in the opinion of the investigator, detected on ECG at screening of either rhythm or conduction, QTcF >450 ms, or a known long QT syndrome.
7. Underwent major surgery within 3 months prior to the baseline visit or have major surgery planned during the study period.
8. Criterion modified per amendment.
  - 8.1. Unstable cardiovascular, pulmonary, or other disease (other than systemic sclerosis-related), in the opinion of the investigator, within 6 months prior to the baseline visit (e.g. coronary heart disease, heart failure, stroke).
9. Previous or planned hematopoietic stem cell transplantation.
10. Subjects on phototherapy within 6 weeks prior to the baseline visit.
11. Severe pulmonary disease with FVC  $\leq$ 45% of predicted within 6 months prior to the baseline visit.
12. Chronic or ongoing active infectious disease, including tuberculosis (requiring hospitalization or systemic treatment within 4 weeks prior to the baseline visit).
13. Criterion modified per amendment.
  - 13.1. Taking medication known to be a substrate mainly metabolized by CYP2C8 ([Appendix 1](#)) within 4 weeks or 5 half-lives of the drug (whatever is longer) prior to the baseline visit.
14. Criterion modified per amendment.
  - 14.1. Taking medication known to be strong inducers of CYP3A4 and also including St. John's Wort ([Appendix 2](#)) within 4 weeks or 5 half-lives of the drug (whatever is longer) prior to the baseline visit.
15. Criterion modified per amendment.
  - 15.1. Taking medication known to be strong inhibitors of CYP3A4 ([Appendix 3](#)) within 4 weeks or 5 half-lives of the drug (whatever is longer) prior to the baseline visit.

16. Criterion modified per amendment.
  - 16.1. Taking medication known to be potent inducers of P-gp ([Appendix 2](#)) within 4 weeks or 5 half-lives of the drug (whatever is longer) prior to the baseline visit.
17. Criterion modified per amendment.
  - 17.1. Taking medication known to be potent inhibitors of P-gp ([Appendix 4](#)) within 4 weeks or 5 half-lives of the drug (whatever is longer) prior to the baseline visit.
18. Abnormal liver function test (LFT) at screening, defined as aspartate aminotransferase (AST), and/or alanine aminotransferase (ALT), and/or bilirubin, and/or alkaline phosphatase >2x upper limit of normal (ULN). Retesting is allowed once.
19. Criterion modified per amendment.
  - 19.1. Abnormal renal function at screening, defined as estimated glomerular filtration rate (eGFR) <60 mL/min/1.73 m^2 using the Chronic Kidney Disease Epidemiology Collaboration (CKD-EPI) equation. Retesting is allowed once.
20. Hemoglobin level <10 g/dL at screening. Retesting is allowed once.
21. Concurrent participation or participation in a drug, drug/device, or biologic investigational research study within 5 half-lives of the IMP (or within 8 weeks when half-life is unknown) prior to the baseline visit, or prior participation in an investigational antibody study within 6 months prior to the baseline visit.
22. Gastrointestinal involvement (e.g. unable to swallow) preventing oral administration of IMP.
23. Subjects diagnosed with:
  - Systemic sclerosis sine scleroderma, or
  - Localized scleroderma, or
  - Eosinophilic fasciitis, eosinophilia myalgia syndrome.
24. Diagnosis of another connective tissue disorder by ACR criteria.
25. History of diverticulosis requiring antibiotic treatment or any other gastrointestinal condition that might predispose to perforations.
26. Investigator or other study staff or relative thereof who is directly involved in the conduct of the study.
27. Significant blood loss (including blood donation [ $>450$  mL]), or transfusion of any blood product within 12 weeks prior to the baseline visit.
28. Active drug or alcohol abuse (more than 3 glasses of wine or beer or equivalent/day) within 2 years prior to first IMP intake.
29. Any other clinical condition or circumstances that in the opinion of the investigator may make a subject unsuitable for inclusion or unable to complete the study or comply with study procedures and requirements.
30. A history of being admitted to an institution under an administrative or court order, if applicable by local legislation.

### 4.5.3. Prohibition and Restrictions

#### 4.5.3.1. Precautions for Sexual Intercourse

Highly effective contraceptive measures for both males and females of childbearing potential must be documented in the source documents.

#### 4.5.3.1.1. *Female subjects*

In line with the Heads of Medicines Agencies (HMA)'s Clinical Trial Facilitation Group (CTFG) recommendation, female subjects are considered of non-childbearing potential if they meet one of the following criteria:

- No menses for 12 or more months without an alternative medical cause. A high follicle stimulating hormone (FSH) level in the postmenopausal range may be used to confirm a postmenopausal state in women not using hormonal contraception or hormonal replacement therapy. However in the absence of 12 months of amenorrhea, a single FSH measurement is insufficient.
- Permanently surgically sterile (bilateral oophorectomy [i.e. surgical removal of ovaries], bilateral salpingectomy, or hysterectomy [i.e. surgical removal of uterus]).

All other female subjects are considered to be of childbearing potential (WOCBP) and must use one of the following highly effective methods of birth control prior to the first dose of IMP, during the clinical study and for at least 30 days after the last dose of IMP:

- Combined (estrogen and progesterone containing) (oral, intravaginal, transdermal) hormonal contraception associated with inhibition of ovulation plus a barrier method.
- Progesterone-only hormonal (oral, injectable, implantable) contraception associated with inhibition of ovulation plus a barrier method.
- Intrauterine device.
- Intrauterine hormone-releasing system.
- Bilateral tubal occlusion.
- Sexual abstinence defined as refraining from heterosexual intercourse during the entire period of risk associated with the study treatments. The reliability of sexual abstinence needs to be evaluated in relation to the duration of the clinical study and the preferred and usual lifestyle of the subject.

Periodic abstinence (e.g. calendar, symptothermal, post-ovulation methods), declaration of abstinence for the duration of a clinical study, withdrawal, spermicides only, and lactational amenorrhea method are not acceptable as methods of contraception.

In case a WOCBP has a vasectomized partner, provided that partner is the sole sexual partner of the WOCBP clinical study participant and that the vasectomized partner has received medical assessment of the surgical success, then she is not required to use an additional form of contraception.

Within these limits, the specific forms of contraception employed are left to the discretion of the subject, the investigator, and/or the subject's physician.

WOCBP will be requested to do a monthly urine pregnancy test during the treatment period, and a urine pregnancy test at the Follow-up Visit 1. The monthly pregnancy test for Weeks 12 and 20 will be performed at home by the subject using home testing kits. The site will construct the subjects on how to use and read the pregnancy tests. The outcome must be documented on the subject diary card and the site will obtain the results during the phone call and record in the source and case report form (CRF). In case of a positive urine pregnancy test at home, the subject should immediately contact the clinical study center and the investigator

---

 As there is no current data available regarding potential interactions between IMP and hormonal contraceptives, female subjects who use hormonal contraception should supplement this with a barrier method (preferably male condom).

must report this immediately, and under no circumstances later than 24 hours after being made aware.

The safety of GLPG1690 during breastfeeding is unknown. Women who are nursing are not allowed to take part in this clinical study.

#### **4.5.3.1.2. Male subjects**

Men should be advised not to father a child while receiving treatment and must use effective contraception during and up to 90 days after treatment. Male subjects intending to father a child, should discontinue treatment with IMP and wait for at least 90 days before stopping the contraceptive measures detailed in this section.

Non-vasectomized male subjects with female partners of childbearing potential must be willing to use a condom from the time of the first dose of IMP, during the clinical study, and for at least 90 days after the last dose of IMP, in addition to having their female partner use one of the following forms of contraception:

- Combined (estrogen and progesterone containing) (oral, intravaginal, transdermal) hormonal contraception associated with inhibition of ovulation.
- Progesterone-only hormonal (oral, injectable, implantable) contraception associated with inhibition of ovulation.
- Intrauterine device.
- Intrauterine hormone-releasing system.

Sexual abstinence defined as refraining from heterosexual intercourse during the entire period of risk associated with the study treatments is considered a highly effective contraceptive measure. The reliability of sexual abstinence needs to be evaluated in relation to the duration of the clinical trial and the preferred and usual lifestyle of the subject.

Periodic abstinence (e.g. calendar, symptothermal, post-ovulation methods), declaration of abstinence for the duration of a clinical study, withdrawal, spermicides only, and lactational amenorrhea method are not acceptable methods of contraception.

In a case where the female partner of a male participant has undergone documented surgical sterilization that was performed more than 1 year before screening, then the subject is not required to use an additional form of contraception.

Vasectomized male subjects with female partners of childbearing potential are not required to use an additional form of contraception providing that surgical sterilization has been successful (documented azoospermia by semen analysis).

No sperm donation is allowed from first dose of IMP, during the clinical study, and until 90 days after the last dose of IMP.

#### **4.5.3.2. Prior and Concomitant Medications**

##### **Prior Medication**

Prior medication taken up to 12 weeks prior to and during the screening period will be recorded after signing of the ICF, at Visit 1.

## Concomitant Medication

Should any treatment other than the IMP be used during the course of the study, the name of the medication, the dosage, the route, the reason for medication, and the start and stop dates of administration must be recorded in the CRF until Follow-up Visit 2.

Concomitant medications taken for the long-term treatment of pre-existing conditions can continue during the study, provided they are in accordance with the in- and exclusion criteria (see Sections 4.5.1 and 4.5.2, respectively). It is required that these medications are stabilized prior to study entry (8 weeks prior to screening, or longer if  $t_{1/2}$  and/or time to reach steady state of the drug requires) and preferably continue without variation of dose or regimen during the study.

In case additional concomitant medication needs to be administered or dose adjustments for pre-existing conditions need to be performed during the study, the benefit-risk to the subject should be carefully assessed and consideration given to the timing of any necessary introduction of new medications.

The following medications are prohibited within 4 weeks prior to the baseline visit and during the treatment period: warfarin, antifibrotic agents (including colchicine, minocycline, tyrosine kinase inhibitors [nilotinib, imatinib, dasatinib, nintedanib], pirfenidone), bosentan or Type 1 oral collagen. The following medications are prohibited within 3 months prior to the baseline visit and during the treatment period: steady dose of prednisone or its equivalent >10 mg/day, methotrexate >20 mg/week, azathioprine >150 mg/day, MMF >3 g/day, mycophenolic acid >2.16 g/day, leflunamide >20 mg/day. Cyclophosphamide is prohibited within 6 months prior to the baseline visit and during the treatment period, as well as the following biologics: tocilizumab or other drugs targeting IL-6/IL-6 receptor, abatacept, anti-tumor necrosis factor (TNF) drugs, rituximab, belimumab, or other monoclonal antibodies.

If during the study, the subject's condition necessitates the use of one of the abovementioned medications (excluding prednisone or its equivalent >10 mg/day), the use of IMP should be interrupted until resolution or stabilization of this condition, preferably after consultation with the contract research organization (CRO) medical monitor (as per study contact list) or sponsor's study physician (if the former is not available).

### Precautions with concomitant medication known to prolong the QT interval

The use of medication known to prolong QT interval during the study needs to be based on a benefit-risk evaluation by the investigator, e.g. in the case of atrial fibrillation. In certain other situations (e.g. the initiation of macrolides or fluoroquinolones in case of a lower respiratory tract infection), when the benefit-risk evaluation necessitates the administration of medication known to or potentially prolonging QT, IMP can be interrupted as evaluated by the investigator after clinical assessment of the subject's profile, including the baseline QTcF and how this has changed over time for this specific subject. If the investigator elects to continue IMP, additional monitoring will be performed as per investigator's judgment. A nonexhaustive list of medication known to prolong QT interval is provided in [Appendix 5](#). Note: In case QT interval prolongation is reported in a subject while receiving one of these medications, the investigator should follow the labels and Risk Evaluation and Mitigation Strategies guidance.

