### **QT Interval Prolongation**

The potential effect of GLPG1690 on QT interval prolongation is not fully known. Consequently, subjects with long QT syndrome or QTcF >450 ms during screening will be excluded. The chronic use or initiation of medication known to prolong the QT interval needs to be evaluated on a case-by-case basis. Periodic ECG recording and monitoring with central reading will be implemented for the duration of the study. A list intended as guidance for the investigator is provided in [Appendix 5](#).

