### Precautions with other concomitant medications

At dose levels of 600 mg q.d., GLPG1690 has the potential to substantially influence the metabolism of CYP2C8 substrates and to potentially be influenced by known strong CYP3A4/potent P-gp inducers/inhibitors.

- GLPG1690 demonstrated a strong time-dependent inhibition potential against CYP2C8-mediated metabolism. Consequently, GLPG1690 should not be used concomitantly with medications primarily or solely metabolized via CYP2C8 (see [Appendix 1](#)). For other medications involving part of their metabolism pathway via CYP2C8, caution should be applied on a case-by-case basis taking into consideration the benefit-risk ratio. Statins such as fluvastatin and pitavastatin are metabolized to some degree by CYP2C8, and need to be used with caution. Other statins such as simvastatin, lovastatin, and atorvastatin are theoretically less metabolized by CYP2C8. Monitoring of LFTs and creatine kinase is implemented during the study, and guidance to the subject aligned with guidance for statins in clinical practice is therefore strongly recommended. Loperamide is also a substrate of CYP2C8, and special caution should be applied in alignment with clinical practice.
- GLPG1690 is a substrate of CYP3A4 and P-gp, and could therefore be influenced by their respective inhibitors and inducers. GLPG1690 exposure is reduced up to 90% by the strong CYP3A4/potent P-gp inducer rifampin. As a consequence, strong inducers of CYP3A4 and/or P-gp are part of the exclusion criteria and should be avoided during the study to ensure proper exposure to GLPG1690 (see [Appendix 2](#)). For inhibition, strong CYP3A4 and dual strong 3A4 and potent P-gp inhibitors have shown that GLPG1690 exposure increased by 3 to 4 fold when coadministered, therefore use of known strong CYP3A4 inhibitors and potent P-gp inhibitors is prohibited during the study (see [Appendix 3](#) and [Appendix 4](#)). Antibiotics from the macrolide therapeutic class are excluded, unless they are used for the short-term treatment of a lower respiratory tract infection with interruption of IMP, which is restarted as soon as possible after the completion of the treatment with macrolides.

It is highly recommended that the CRO medical monitor (as per study contact list) or sponsor's study physician (if the former is not available) are consulted before the initiation of medication known to prolong QT interval, to be a CYP2C8 substrate, or to inhibit or induce P-gp/CYP3A4.

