In certain situations, when the benefit-risk evaluation necessitates the administration of medication excluded from use during the study, the use of IMP should be interrupted until resolution or stabilization of this condition, preferably after consultation with the CRO medical monitor (as per study contact list) or sponsor's study physician (if the former is not available) and restarted as soon as possible.

As a rule, inclusion of subjects with stable chronic illness on stable medications which are metabolized/transported by the abovementioned CYP/transporter enzymes should be decided on a case-by-case basis if not excluded or prohibited, taking into account the medical history, concomitant medication of the subject, the therapeutic index of the medication, and safety profile.

As indicated in the study contact list, the CRO medical monitor should be contacted, or the sponsor's study physician in case the former is not available (when deemed necessary by the investigator), specifically for medication with a narrow therapeutic index and/or a risk of (un)predictable AEs.

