### 6.6.5. 12-lead Electrocardiogram

At the time points specified in the Schedule of Activities (see Section 6.11) a 12-lead ECG will be recorded and results will be sent for central reading. Triplicate ECGs will be performed irrespective of IMP intake at Visit 1 (screening), within 30 minutes before IMP intake and between 2 to 3 hours after IMP intake at Visit 2 (baseline) and Visit 3. A single ECG will be performed within 30 minutes before IMP intake at Visits 7 and 9, and irrespective of IMP intake at ED (if applicable) and Follow-up Visit 1. The ECG must be taken after subjects rested for at least 5 minutes in the supine position. In case an indwelling catheter is used, ECGs may be recorded after blood sampling, provided that there is at least 30 minutes between catheter insertion and the ECG recording. When catheter insertion would fail, the 12-lead ECG needs to

be taken before the venipuncture and at least 30 minutes after the failed attempt. Triplicate ECGs will be performed preferably within a time span of 6 minutes, with an approximate 2-minute interval between ECGs. Parameters to be recorded include the following: heart rate, PR interval, QRS interval, uncorrected QT interval, morphology, and rhythm analysis. QTcF will be considered as normal if  $\leq 450$  ms, while a prolongation of QTcF to  $\geq 500$  ms or an increase from baseline  $>60$  ms will be considered a threshold of concern. Immediately after recording, the ECG will be reviewed by the investigator on clinically significant abnormalities. This immediate review during the visit needs to be documented in the subject's source. After receipt of the central report, also all flagged ECG abnormalities need to be assessed by the investigator on clinical relevance. Clinically significant abnormal values should be recorded as AEs.

[REDACTED]

[REDACTED]

[REDACTED]

[REDACTED]

[REDACTED]

[REDACTED]

[REDACTED]

[REDACTED]

[REDACTED]

[REDACTED]

[REDACTED]

[REDACTED]

[REDACTED]

[REDACTED]

[REDACTED]

[REDACTED]

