## APPENDIX 4: KNOWN POTENT P-GP INHIBITORS

Excluded medication:

Amiodarone
Azelastine
Azithromycin – Clarithromycin – Erythromycin – Roxithromycin – Telithromycin (unless used under the condition described in Section 4.5.3.2 )
Cyclosporine
Itraconazole - Ketoconazole
Tamoxifen
Verapamil

This list is intended as a guidance for the investigator.

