## **APPENDIX 5: MEDICATION KNOWN TO PROLONG QT INTERVAL**

This is based on the CredibleMeds list of medication known to prolong QT interval/cause Torsade de Pointes (Woosley RL. et al., 2018).

Medication to be used with caution:

Disopyramide
Dofetilide
Flecainide
Ibutilide
Quinidine
Sotalol
Hydroxychloroquine

This list is intended as a guidance for the investigator.

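### Section 4.5.3.2 makes pausing IMP optional when a macrolide is started for a lower respiratory tract infection, while the next subsection makes pausing a condition of macrolide use

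*Protocol*

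**What the plan says.** Protocol Section 4.5.3.2 treats macrolides in two adjacent subsections.

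- **QT subsection.** Its example is "the initiation of macrolides or fluoroquinolones in case of a lower respiratory tract infection". If benefit-risk calls for such a drug, the investigator may pause IMP after assessing the subject, including the baseline QTcF and its course. The alternative is also covered: "If the investigator elects to continue IMP, additional monitoring will be performed as per investigator's judgment". The only appendix it cites is Appendix 5.
- **Subsection on other concomitant medications.** Antibiotics of the "macrolide therapeutic class are excluded, unless they are used for the short-term treatment of a lower respiratory tract infection with interruption of IMP", with IMP restarted once the macrolide course is over. It closes with a general rule: where benefit-risk requires "administration of medication excluded from use during the study, the use of IMP should be interrupted until resolution or stabilization of this condition".

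The appendices bear on the same question.

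- Appendix 4 lists five macrolides as excluded potent P-gp inhibitors, "unless used under the condition described in Section" 4.5.3.2.
- Appendix 3 lists two of them, clarithromycin and telithromycin, as excluded strong CYP3A4 inhibitors.
- Appendix 5, headed "Medication to be used with caution", names seven QT-prolonging drugs, none of them a macrolide.

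**The concern.** Both subsections address the same drug class, the same infection and the same decision. One leaves continuing IMP to the investigator; the other allows the macrolide only if IMP is stopped. The QT subsection has no exception for macrolides and no pointer to the next subsection or to Appendices 3 and 4. An investigator who reads it for guidance on a macrolide could continue IMP in good faith and so breach the exclusion.

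What is at stake is the safety of an individual subject. Section 4.4 states: "The potential effect of GLPG1690 on QT interval prolongation is not fully known". Section 2.1.4.1 reports QT prolongation in the dog studies, calling it non-adverse in one sentence and listing it among adverse findings in another. On the other side, Section 2.2.1 reports no clinically significant ECG abnormalities in the Phase 1 studies or in the 12-week study in pulmonary fibrosis. The combination is one the protocol means to avoid; harm from it has not been shown.

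**Working it through.** The point rests on a comparison of texts. The only arithmetic is a set of intervals given as context in step 4.

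**1. Each action tested against each text (macrolide, lower respiratory tract infection)**

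| Text | IMP paused | IMP continued with monitoring |
|---|---|---|
| Section 4.5.3.2, QT subsection | allowed | allowed |
| Section 4.5.3.2, other concomitant medications, macrolide rule | required | not allowed |
| Same subsection, general rule for excluded drugs | called for | departs from it |
| Appendix 4 | meets the exception | exception not met |

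Pausing satisfies every row. Continuing satisfies only the first.

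**2. The same test for a fluoroquinolone.** No fluoroquinolone appears in Appendices 1 to 4, so only the first row applies and both actions are allowed. The continue option therefore has a legitimate use, and the conflict is confined to macrolides.

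**3. Which rule is intended.** The macrolide rule, the general rule for excluded drugs and the two exclusion lists all point to interruption. The subsection on other concomitant medications also gives a reason for prohibiting strong CYP3A4 and potent P-gp inhibitors: GLPG1690 exposure rose 3- to 4-fold with inhibitors of this kind. Only the QT subsection points the other way, and it does so through an example that pairs macrolides with a class that is not excluded.

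**4. Context: scheduled ECGs on treatment.** The stopping rules in Section 4.5.4 act on an ECG recording. Section 6.6.5 schedules ECGs at Visits 2, 3, 7 and 9, which Section 4.1 places on Days 1, 15, 113 and 169. For the later visits: "A single ECG will be performed within 30 minutes before IMP intake at Visits 7 and 9". Section 6.1 gives standard windows of ±2 days for Visit 3 and ±4 days for Visits 7 and 9.

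- Visit 3 to Visit 7: 113 − 15 = 98 days. With windows, (113 − 4) − (15 + 2) = 92 to (113 + 4) − (15 − 2) = 104 days.
- Visit 7 to Visit 9: 169 − 113 = 56 days. With windows, (169 − 4) − (113 + 4) = 48 to (169 + 4) − (113 − 4) = 64 days.

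If a macrolide were given with IMP inside one of these intervals, a QTcF change would be seen only on an ECG that the investigator arranged.

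**The case against.** The strongest reply is that restrictions in a protocol are cumulative. A drug can raise both a QT concern and an interaction concern, and the stricter rule then governs. The QT subsection is a general precaution in which macrolides appear only as an example. The specific class rule follows immediately, within the same numbered section, and it is the only text there that sets a condition for macrolide use, so it must be what Appendix 4 refers to. A site would have to read the QT subsection alone, overlook the next subsection and both appendices, and skip the medical-monitor consultation that the protocol strongly recommends. If IMP were continued, additional monitoring is still to be done; only its form is left to judgment. There are also on-site visits at Weeks 4 and 8, safety calls at Weeks 12 and 20, and diary recording of medication changes.

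Most of this stands, and it keeps the point small. It does not remove it. The cumulative reading is reasonable, but the protocol does not state it. The consultation is advised rather than required. The QT subsection does more than omit a detail: for a named example it describes a course of action that the next subsection prohibits.

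**Conclusion.** The inconsistency is real and minor. It rests on one reading: that the sentence on electing to continue IMP applies to the situations named just before it, of which a macrolide for a lower respiratory tract infection is the first. The text gives no reason to read it otherwise.

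A reader might infer more than the documents support.

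- **That the ECG intervals measure the risk created here.** They do not. They are the ordinary schedule for every subject, would be unchanged after correction, and apply equally to permitted fluoroquinolone use.
- **That a macrolide would raise exposure 3- to 4-fold.** The documents give no exposure figure for any macrolide. Section 2.2.3 reports AUC 3-fold with itraconazole and 4-fold with voriconazole. Cmax rose 1.4-fold with either drug, an increase the protocol regards as unlikely to matter clinically. The effect of a macrolide is unknown.
- **That the efficacy results are affected.** No endpoint, estimate or analysis depends on this wording.

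How many of the approximately 30 subjects might need a macrolide cannot be derived from the documents.

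**What to change.** Keep macrolides in the QT subsection, since Appendix 5 names none, and add after the sentence on electing to continue IMP:

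> For macrolides, IMP must be interrupted for the duration of the macrolide course, as described in the next subsection and Appendices 3 and 4; the option to continue IMP with additional monitoring does not apply to macrolides.

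Do not widen the sentence to every drug in Appendices 1 to 4. Appendix 2 lists prednisone or equivalent above 10 mg/day, which the concomitant-medication text of Section 4.5.3.2 exempts from its interruption rule. A blanket requirement would also sit badly with the rescue-medication rule, which leaves continuation of IMP to case-by-case decision when the disease worsens.

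Send sites a reminder of the macrolide rule now; it is already protocol text. The added sentence is a protocol amendment and needs ethics committee review and approval before use (Section 10.4.1), so bundle it with the next amendment. The cost is administrative: one sentence and a site notice, with no new visit, procedure or data collection.
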